4.2 Recruitment, screening and informed consent procedure

Recruitment:

Patients will be recruited at their admission to the ED during the triage process. Inclusions will be done on working days and hours.

The participating sites will identify all eligible patients. The investigator and the research staff will approach each potential patient and inquire about their interest and eligibility in participating in this study. This inquiry will include screening questions to confirm eligibility as well as a description of the study and responsibilities for participating. All enrolled patients should be followed up within the study, except if their participation is prematurely terminated.

The recruitment period will be up to 2 years, during which 500 patients are planned to be enrolled, which means between 1 to 2 patients per site and per week. If the enrolment goals are not met, the study will be extended until achievement. The recruitment is competitive between the sites.

Emergency situation (HRA, Art. 30-31 and OClin Art. 15)

This study is carried out in an emergency situation and the expected results can only be achieved in an emergency situation. Indeed pneumonia is a major cause of morbidity and mortality and of antibiotic prescription in hospitalized patients whom prognosis is engaged. Making the diagnosis and the decision of treating the patient consulting the ED must be performed within first hours (the international guidelines recommend treating the patient while he/she is still in the ED for a suspicion of pneumonia).

Description of the informed consent process (HRA, Art. 7, 16, and 18, 42; ClinO, Art. 7 - 9) including time for consideration given to the participants:

The investigators will explain to each participant/or their representative the nature of the study, its purpose, the procedures involved, the expected duration, the potential risks and benefits and any discomfort it may entail. Each participant or their representative will be informed that the participation in the study is voluntary and that he or she may withdraw from the study at any time and that withdrawal of consent will not affect his or her subsequent medical assistance and treatment. The participant or his/her representative will be informed that the medical records may be examined by authorised individuals other than their treating physician.

Consent:

- The patient has his ability to consent in the emergency room: he signs the standard consent for participant.
- The patient has not his ability to consent in the emergency room
 - o he does not express either orally or by any particular behaviour his/her refusal of being part of the research project.
 - o a physician independent of the study will be sought to defend the interest of the patient (HRA 30-31) and sign the dedicated written confirmation

Everything will be done to establish the will of the patient as soon as possible

- o the patient recovers his capacity during hospitalization : he signs the standard consent for participant.
- o the patient is known to no longer have the ability to consent or does not recover his ability to discern during hospitalization: the relative/legal representative sign the dedicated consent.

CIRCUS: an information letter will be given to the clinician in charge of the patient at the ED (appendix).

GEROBIOTA

The patient will be able to participate to **GEROBIOTA** in Geneva and Bern. He will also be asked to give his consent to participate to the **biobank**.

Pneumoscope

The patient will be able to participate to **this ancillary study** when included in Geneva.

4.3 Study procedures

3 years (2 years of recruitment plus 3 months of follow-up for OCTOPLUS and one year for GEROBIOTA), inclusions on working days and hours (see Figure 1)

CXR will be interpreted in real-time by a first radiologist and a CRF will be filled in, including the probability of pneumonia.

LDCT will be interpreted in real-time by another radiologist and a CRF will be filled in, including the probability of pneumonia. Both will be blinded to the other's interpretation.

LUS will be performed by another clinician than the one in charge of the patient, and his practice of LUS will be standardized before the launching of the study.

After identification in the ED, included patients will be randomized 1:1:1 to one of the following three arms (stratified by participating center):

-Only CXR (image and CRF) will be available to the clinician (control arm). LDCT and LUS will be performed but not available (clinician will be blinded to LDCT and LUS)

-Only LDCT (image and CRF) will be available to the clinician (first intervention arm). CXR and

LUS will be performed but not available (clinician will be blinded to CXR and LUS)

-Only LUS (image and CRF) will be available to the clinician (second intervention arm). CXR and LDCT will be performed but not available (clinician will be blinded to CXR and LDCT)

The blinding will be maintained during the first 5 days, and hence will not influence the diagnosis and the treatment of the patient.

Before discharge of the ED, the clinician in charge will be asked to assess on a 3-level Likert scale the probability of pneumonia (high, intermediate, low level) while considering all available clinical and biological data, plus the imaging modality according to the randomization arm.

He will document the intended treatment strategy (antibiotic prescription or not, which molecule, for which indication if not for pneumonia, intended duration).

He will be allowed to prescribe antibiotic for another indication than pneumonia by documenting a principal alternative diagnosis (e.g. urinary tract infection, acute exacerbation of a chronic obstructive pulmonary disease, cardiac failure...) and strongly encouraged not to prescribe antibiotic for pneumonia if he rated a low probability of the disease.

Patients will be followed-up daily during the hospitalization by research staff and by phone up to 3 months to assess readmission as well as mortality.

A panel of experts will adjudicate the final diagnosis in all patients, having access to all data (clinical, CXR, LDCT and LUS and outcome data at day 28), while blinded to the allocation arm. Their diagnosis will be considered as the reference diagnosis.

Safety: Number of death and admissions to the ICU in each arm will be communicated to a dedicated data safety monitoring board after 200 inclusions for a safety interim analysis.

Blinding of the imaging modalities: For each patient, the two blinded imaging modalities will be registered on a secured PACS. The CRFs filled for these imaging modalities will be kept unavailable as well as images until day 5.

Unblinding: The research staff will ensure that unblinding of imaging and CRFs is done at day 5 and that all results are available in the electronic health record.

Unblinding will be performed **in emergency** at the ED if the radiologist/clinician performing LUS diagnoses immediately life-threatening findings: pneumothorax, pleural effusion in large quantities (white lung) with mediastinal shift, complete atelectasis of one lung, indirect sign of aneurysmal rupture (haemomediastinum), massive pericardial effusion, tracheal foreign body, pneumoperitoneum, haemothorax, pneumomediastinum, suspicion of acute tuberculosis (NB: pulmonary embolism won't be excluded as LDCT will be performed without intravenous contrast).

In case of such finding, the radiologist interpreting CXR or LDCT and the clinician performing LUS will call in emergency the investigator to be allowed to communicate the results to the clinician.

In case of subsequent clinical deterioration, the clinician in charge of the patient may prescribe any new imaging deemed necessary: a new CXR for the diagnosis of heart failure; injected chest CT scan to eliminate a pulmonary embolism or a suppurative complication.

Nevertheless, the local investigator will be accessible and able to proceed to a deblinding in justified cases.

GEROBIOTA

At admission:

-Microbiota samples (saliva and respiratory samples) before antibiotic administration at the ED if possible. They will be stored at -80.

NB: respiratory samples will be those taken for routine methods including sputum, induced sputum, tracheal aspirate or broncho-alveolar lavage if done and still available

-Blood: Serum (2 tubes), plasma EDTA (2 tubes), plasma citrate (2 tubes), PAX gene DNA (1 tube), PAX gene RNA (1 tube).

During hospitalization:

- Oral health examination by a medical dentist as soon as the patient is stabilized (≈ 30 min)
- Geriatric assessment by the research staff during the first week of hospitalization (≈ 45 min)

At discharge: 2 tubes of serum, 4 tubes of plasma

Table 1: Timeline of patient enrolment/allocation, interventions, and assessments

Study periods	Screening	Inclusion	Discharge from the ED	Discharge from the acute setting	1 month	3 months	Reference diagnosis
Visit	1	2	3	5	6	7	8
Time (day)	From the ED admission until the ED discharge (D0).			d15	d30	d90	
Windows (days)	NA	NA	NA	-2/+5	-2/+10	-2/+15	NA
Patient/representative IC or independent physician	x						
In-/exclusion criteria	x						
Randomization		x					
Demographics		x					
Medical history		x					
Physical examination	x						
Vital signs							
Time to clinical stability	x	x	x	x			
Laboratory tests	x						
CXR, LDCT, LUS		x					
Main diagnosis, other diagnosis, and therapeutic outcomes before ED discharge				x			
No. of days of AT prescription			x				
Other diagnosis outcomes				x			
Clinical outcomes (safety outcomes)				x	x	x	
QoL questionnaire		x		x		x	
Panel of experts							x

AT = antimicrobial therapy, CXR = chest x-ray, ED = emergency department, IC = informed consent, LDCT = low-dose computed tomography, LUS = lung ultrasonography, QoL = quality of life

Table 1 bis: GEROBIOITA

Study period	Inclusion	Hospitalization	Discharge	1-year
Biobank	x		x	

Geriatric and oral health assessment		x (once)		
Phone call				x

Table 2 : Interventions in both studies

OCTOPLUS	GEROBIOTA
CXR, LDCT and LUS	Blood (30 ml), saliva, respiratory samples (biobank) at admission
Follow-up during the hospitalization by the research staff	Oral health assessment and Geriatric assessment during hospitalization
Phone call at 1 and 3 months	Saliva and blood (6 tubes) (biobank) before discharge
	Phone call at 1 year

Measures taken to reduce biases:

-Blinding of patients, attending physicians, investigators:

- the clinician in charge will know the allocation arm but will be blinded to the results of the two other exams
- the radiologist interpreting LDCT will not have access to CXR and LUS
- the clinician performing LUS will have access to the electronic file (including clinical data) but not to CXR and LDCT
- the participants will be blinded, meaning they will know their diagnosis but not the allocation arm
- the panel of experts will be blinded to the arm of allocation and to the probability of pneumonia according to the clinician to perform the final review
- the investigators will be blinded to the allocation arm

-Blinding of outcomes assessment and data analysis:

Clinical data on all included patients will be collected by the study personnel and recorded in the CRF and database. HUG data managers experienced in generating blinded reports will then provide data exports to a blinding outcomes assessor and a blinded data analyst. These exports will contain recoded study identification numbers and no information on diagnostic assignments allowing for both fully blinded outcomes assessment and data analysis. For analyses, data management will be asked to export data with only coded treatment group labelling.

-Blinding of the imaging results:

As explained above, these blinded results will be available on a research PACS until day 5, when the research staff will proceed to unblinding.

4.4 Withdrawal and discontinuation

Withdrawal:

If a patient wishes to withdraw consent, the investigator will be informed, and the patient will be excluded from the study without any consequence on his care.

As the validity of the clinical trial or its results could be distorted in essential points by the destruction of biological material and personal health-related data, their use in the clinical trial will be allowed despite the refusal of the patient. Since pneumonia is very frequent in elderly patients and since this population is very rarely included in clinical trials, we think it is very important to carry out this trial and not to destroy data which would be valuable for further elderly patients having pneumonia.

In case of protocol violation, the patient will stay in the randomized arm for the intention to treat analysis and will be excluded from the arm for the per protocol analysis. If the patient gets lost to follow-up, the data will be censored after the last visit. In case of death, the civil registry will be consulted regarding the information on mortality.

Death of the patient:

In case of death before obtaining provisional consent, there will be no inclusion.

In case of death of the person after provisional consent, it will be verified whether the patient has issued Advance Directives authorizing the use of data or biological materials for research purposes. If this is not the case, the consent of the representative will be necessary.

5. STATISTICS AND METHODOLOGY

5.1. Statistical analysis plan and sample size calculation

Methodology

[name]; Investigation Unit, Geneva University Hospitals, [name], Switzerland, Email: [contact], [contact]

We hypothesize that the proportion of patients with a correct diagnosis of pneumonia (proportion of true positive plus true negative) will be higher in LDCT arm than in CXR arm. The null hypothesis that will be tested in the primary analysis is the equality of proportion of correctly classified patients in LDCT and CXR arm.

The analysis will follow the intention to treat principle. A sensitivity analysis will be conducted on the per protocol population (i.e. excluding patients who have not received the allocated intervention, and patients who crossed over). Another sensitivity analysis will be conducted excluding patients who will have had CXR before LDCT and LUS.

The diagnosis made by the panel of experts will be the reference diagnosis for calculation of the primary outcome in each arm, and to determine diagnostic accuracy expressed as sensitivity, specificity, predictive values and likelihood ratios. The primary outcome in each arm will be compared to the two other ones.

Primary analysis

The reference diagnosis will be positive (respectively “negative”) if the panel of experts rates the probability of pneumonia diagnosis “intermediate” or “high” (respectively “low”) on the Likert scale. The clinician’s diagnosis will be positive (respectively “negative”) if the clinician rates the probability of pneumonia diagnosis “intermediate” or “high” (respectively “low”) on the Likert scale. We will assume an adequate diagnosis classification, if the clinician’s diagnosis and the reference diagnosis (panel of experts) agree (true positive and true negative diagnoses). The proportions of correctly classified patients in the LDCT and CXR arms will be calculated with 95% Clopper-Pearson confidence intervals (CIs), and will be compared with a logistic regression model adjusted for sites to account for the stratified randomization. The statistical test will be two-sided and the significance threshold will be 0.05.

Secondary analyses

1) The proportion of adequate diagnoses in the LUS arm will be also calculated with the 95% Clopper-Pearson CI, and will be compared with the CXR arm using a logistic regression model adjusted for sites.

2) Similarly, the proportion of adequate diagnoses in the LUS arm will be compared with the LDCT arm.

3) The sensitivity (proportion of positive diagnoses among patients with a positive reference diagnosis) and specificity (proportion of negative diagnoses among patients with a negative reference diagnosis) will be also calculated with 95% Clopper-Pearson CIs in each arm. The

sensitivity between the LUS and CXR arms and between the LUS and LDCT arms will be compared using a logistic regression model adjusted for sites.

4) Positive and negative predictive values, and likelihood ratios will be calculated with 95% Clopper-Pearson CIs in each arm.

5) As a sensitivity analysis, the primary and secondary analyses 1) to 4) will be repeated, whereby only the level "high" on the Likert scale is regarded as positive diagnosis (clinician's diagnoses and reference diagnoses).

6) Treatment outcomes: The cumulative incidence of antibiotic free patients will be investigated over 30 days by using a non-parametric competing risk model with death before antibiotic intake as a competing event and will be compared between arms. Comparisons will be stratified on sites.

As a sensitivity analysis, this analysis will be repeated excluding exacerbation of COPD, where the need for antibiotic therapy is still debated.

7) Diagnosis outcomes: We will describe each of the alternative diagnoses by frequencies in each arm, and the percentage of patients with an alternative diagnosis consistent between radiologists and experts will be evaluated. 95% Clopper-Person CIs will be reported. The proportions of imaging results needing unmasking and of additional radiological studies (and invasive procedures) during the 2 first weeks will be also reported with their 95% Clopper-Pearson CIs. A post-hoc procedure will be applied for pairwise comparisons.

8) Clinical outcomes: We will use Kaplan Meier's estimates to evaluate the time to clinical stability over 15 days in each arm, and a log-rank to compare them. Patients who die in the first 2 weeks will be censored at day 15 (i.e. considered has never reaching clinical stability). The Mann-Whitney test will be used to compare the length of hospital stay between the groups. The proportion of patients with an unplanned transfer to the ICU or operating room will be reported by arm and compared between the arms using a logistic regression model adjusted for sites. All-cause mortality during the 3-month follow-up will be investigated with Kaplan Meier's survival curves, and compared between the arms using a log-rank test stratified on sites. Readmissions during the 3-month follow-up will be investigated using survival models with competing risk. Death before readmission will be the competing event.

9) Cost outcomes: Mean cost per patient will be assessed and compared between arms using multiple linear regression models adjusted for sites. Reweighted estimators will be used to account for censoring.

10) Interagreement rate for the probability of pneumonia rated on a 3-level Likert scale: the agreement between raters participating to the trial and a consensus of two experts will be investigated by using kappa statistics.

11) The association between biological markers (CRP and PCT) and infiltrates will be assessed by differences in the mean levels of markers between patients with and without infiltrates and tested by using t test. Transformations on markers will be applied if needed. Multiple linear regression models will be used for adjustment. Similar methods will be used to investigate the association between markers and the probability of pneumonia rated on the 3-level scale. The analyses will be conducted for each arm.

Interim and safety analyses

There will be no comparative analysis for efficacy or futility. An initial safety analysis will be performed after 200 patients have reached the 1-month follow-up. The study's data manager will ensure that the data will be exported with "scrambled" allocation labels and that study investigators do not have access to the data. The results will be transmitted to the principal investigators and the safety monitoring board. The latter will be free to lift the blind if deemed necessary, and will be asked to make the final decision on the continuation of the study without modification, or terminating the study.

Sub-group analyses

The primary analysis and the secondary analyses related to the assessment of diagnostic performances (secondary analyses 1) to 4)) will be conducted in sub-groups of patients: 1)

patients aged less than 80 years versus patients aged over 80 years, 2) patients with a positive PCR (i.e. detection of a virus) at the beginning of the study versus patients with a negative PCR.

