3.2 Primary and secondary endpoints

Primary outcome measure:

The primary outcome will be the difference in accuracy between LDCT and CXR, assessed at the end of the ED evaluation, using the expert panel as the reference standard, accuracy being computed as (true positive + true negative cases) / (true positive + true negative + false positive + false negative cases).-

Main secondary outcome measures:

Diagnostic outcomes:

- Difference in accuracy between LUS and CXR, assessed at the end of the ED evaluation, using the expert panel as the reference standard
- Sensitivity, specificity of CXR, LDCT and LUS
- Number of additional imaging studies and invasive procedures prescribed during the acute setting
- Prevalence of viral pneumonia
- Prevalence of unmasked imaging results (for an emergency finding)
- Prevalence of incidentalomas

Treatment outcomes:

- Number of antibiotic free days at day 30

Clinical outcomes:

- Time to clinical stability during the first 2 weeks (number of days from admission to the first time all of the following parameters are above/under the threshold value and maintained for a minimum of 24 hours: heart rate <100 beats/min, systolic blood pressure >90 mmHg, temperature <37.8°C (axillary or tympanic), respiratory rate <24 breath/min, oxygen saturation >90% while breathing room air, or need for more than 28% fraction of inspired oxygen to maintain adequate oxygen saturation, resolution of delirium if present at admission)
- Length of hospital stay (in the ED and in the acute setting)
- Proportion of patients with an unplanned transfer to the ICU
- Proportion of patients admitted to rehabilitation or LTCF days through 3 months
- All-cause mortality through 1 month and 3 months
- All-cause readmission to the acute care setting through 1 month and 3 months
- Quality of life at admission, discharge and 3 months (measured by EQ-5D-3L and a CAP score questionnaire)
 - Interagreement rate for the probability of pneumonia between physicians participating to the trial and a consensus of experts in chest imaging, for each method

- Association between biological markers (CRP and PCT) and the presence of an infiltrate

Cost outcomes:

Costs of care, physician, imaging, laboratory, treatment (including antibiotic therapy) and others per patient, health related quality of life until 3 months; unit of work consumption per hospital (number of minutes of care, physician, laboratory and imaging points)

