3.3 Study design

This is a Swiss multicentre superiority randomized clinical study with 3 parallel arms. Randomization will be 1:1:1 using randomly permuted block sizes and be stratified by centre. Patients will be either randomized into the CXR, the LDCT or the LUS arm. The 3 imaging modalities will be performed in all included patients but only one will be available to the clinician according to the allocation arm. The concealed results of the imaging procedures will be unblinded at day 5. The duration of follow-up will be 3 months for OCTOPLUS. The panel of experts will provide their diagnosis a posteriori. An intermediate safety analysis will be performed after 200 patients have completed the 1-month follow-up.

Figure 1: Study design

NB: US performed by a physician not in charge of the patient

Known or potential problems associated with the trial design:

-**Insufficient recruitment:** given the case load of the participating centres and the required sample size, this scenario is unlikely.

-**Risk of the CT:** LDCT is well-tolerated and its mean radiation exposure is much lower than a full-dose CT scan (about 1mSv) (52). In a previous study, a mean (sd) radiation exposure of 1.5 (0.47) mSv was measured, which can be compared to the mean (sd) exposure of conventional CXR of 0.05 (0.03) mSv (20).

-Risk of LUS: there will be many clinicians performing LUS at each site. LUS is known to have a fast-learning curve. To minimize heterogeneity between the clinicians and centres, standardization of LUS practice will be performed in all participating centres before the beginning of the study.

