Finally, we estimated that risks inherent to the trial are minimal and inferior to the benefits of the study which could deliver key results which would provide long-term benefit to all patients with pneumonia.

Sequential realization of the 3 imaging modalities may delay the final working diagnosis of the physician in charge. However, this delay will be minimized by the research staff, who will make any effort to guarantee quick delivery of all diagnostic procedures. As severe pneumonia will not be included, a delay of at most a few hours before adequate treatment is not expected to have a negative impact on patients' evolution (54). All imaging must be done before leaving the ED. A transfer from one ED to another is not considered as an exit from the ED (e.g. a transfer of the 3-Chêne to Cluse-Roseraie for Geneva)

Methods of minimising bias:

-Stratified randomization will be used in this study.

-Allocation sequence

Participants will be randomized 1:1:1 to either the CXR, the LDCT, or the LUS arm as per a computer-generated randomization schedule stratified by study centre using investigator blinded randomly permuted blocks of varying size.

-Concealment mechanism

Patients will be randomized via eCRF directly.

-Implementation

An independent statistician will create confidential randomization lists for each site. The lists will be given to the data-manager to implement the randomization list in the eCRF. Each site will have a dedicated research staff responsible for approaching patients attending the ED regarding inclusion in the study. The triage nurses and the physician working at the ED will also be asked to help the study team by alerting the research staff to the presence of any potential participant. The site's coinvestigator(s) will also be on hand to answer any additional questions the patient might have. If the patient agrees to participate in the study, the patient's written informed consent will be obtained and the study coordinator randomized the patient directly through the eCRF. The research staff will keep the "crosswalk", a table linking the participant's randomization number with his/her identifying data, in a locked document.

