4. STUDY POPULATION AND STUDY PROCEDURES

4.1 Inclusion and exclusion criteria, justification of study population

Patient eligibility criteria

To be eligible for study participation, all patients will be required to meet the following inclusion criteria, and none of the exclusion criteria:

Inclusion criteria

1. Suspicion of community acquired pneumonia (CAP) or nursing-home acquired pneumonia consulting to the ED
2. Age>65 years
3. Signed informed consent
4. Presence of at least one respiratory symptom (new or increasing cough or dyspnoea, purulent sputum, pleuritic chest pain, respiratory rate >20/min, focal auscultatory findings

or oxygen saturation <90% on room air)

5. and at least one sign or laboratory finding compatible with an infection (temperature $>37.8^{\circ}\text{C}$ or $<36.0^{\circ}\text{C}$, CRP $>10 \text{ mg/L}$, PCT $>0.25\mu\text{g/L}$, leukocyte count $>10\text{G/L}$ with $>85\%$ neutrophils or band forms) will be required
presence of acute delirium or unexplained acute fall can substitute for the presence of either the respiratory or the infectious symptom in patients older than 80 years

Exclusion criteria:

1. Need for an immediate admission to the intensive care unit (ICU)
2. Diagnosis of pneumonia in the past 3 months
3. SARS CoV-2 infection diagnosed by PCR or antigenic test within the past 3 weeks and before the arrival to the ED
4. Transfer from another hospital with a diagnosis of pneumonia
5. Thoracic CXR or CT scan or US already performed during the present episode
6. Need for an immediate contrast-enhanced CT
7. Advanced care planning limiting therapy to comfort care only
8. Prisoners
9. Known uncontrolled psychiatric disorders
10. Previous enrollment into the current study

Reasons for inclusion of vulnerable participants:

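### The CRP/PCT–infiltrate association is planned arm by arm although allocation should affect neither variable; one pooled estimate would have a standard error about 1.73 times smaller (minor, free gain in precision)

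*Protocol*

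**What the plan says.** Protocol section 3.2 declares this secondary outcome: "Association between biological markers (CRP and PCT) and the presence of an infiltrate". Section 5.1, item 11, assesses it by "differences in the mean levels of markers between patients with and without infiltrates and tested by using t test", with transformation of the markers if needed and multiple linear regression for adjustment. The item then extends similar methods to the markers and the 3-level probability of pneumonia, and closes with "The analyses will be conducted for each arm". It gives no reason for the split and mentions no pooled estimate.

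On the design, Protocol section 3.3 states: "The 3 imaging modalities will be performed in all included patients but only one will be available to the clinician". Table 1 in section 4.3 marks "Laboratory tests" at screening and randomisation at the later inclusion visit. Under section 4.1, entry requires "at least one sign or laboratory finding compatible with an infection", and CRP and PCT thresholds are on the list of qualifying findings.

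SAP section 1 defers the association of markers with adjudicated pneumonia to a separate SAP. It does not mention the infiltrate analysis, and SAP section 9 does not list that analysis as dropped. Of the documents available, only the Protocol sentence sets the unit of analysis for this outcome.

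**The concern.** An analysis needs splitting by randomised arm when allocation can change one of the variables or the relation between them. Here the exposure is an imaging finding obtained in every patient whatever the arm, and the outcome is a blood value taken before allocation. The question of how CRP and PCT differ between patients with and without an infiltrate has one answer for the trial population. The plan produces three estimates of it, each from a third of the patients.

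What is at stake is precision on a declared secondary outcome. A moderate association that the full data would probably detect could well be missed in a single arm.

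**Working it through.** **The plan's own figure.** The documents give no sample size, standard error or power for the marker analysis. The only stated figure to reproduce is the sample size for the primary comparison (SAP section 3.5): 68% versus 84%, two-sided alpha 0.05, power 90%.

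- Formula: n per arm = [1.960·sqrt(2·0.76·0.24) + 1.282·sqrt(0.68·0.32 + 0.84·0.16)]² / 0.16² = 148 after rounding up. The SAP states 150.
- Power with 150 per arm is 0.904.
- 150 × 1.10 = 165 per arm, and 3 × 165 = 495.

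The arm sizes used below are therefore the plan's own.

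**Does allocation enter either variable?**

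- Marker: Protocol Table 1 puts the blood tests at screening, and CRP and PCT can qualify a patient for entry. Admission values therefore precede randomisation.
- Infiltrate: "The 3 imaging modalities will be performed in all included patients". Protocol sections 3.4 and 4.3 and SAP section 3.1 have each examination interpreted in every patient by someone other than the treating clinician.
- Allocation: "Participants will be randomized 1:1:1 to either the CXR, the LDCT, or the LUS arm". Equal arms therefore have the same expected infiltrate prevalence.

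**Standard error.** Let N be the number analysed and π the proportion with an infiltrate. In units of the marker's SD (after transformation if used):

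SE = sqrt(1/(Nπ) + 1/(N(1−π))) = 1/sqrt(Nπ(1−π))

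In the ratio of one arm to all patients, π and the SD cancel: sqrt(495/165) = sqrt(450/150) = sqrt(3) = 1.732. A simulation (4,000 runs, π = 0.5, true difference 0.3 SD) gave 1.75.

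**Absolute size.** π is not in the documents, so a range of 0.3 to 0.7 is assumed; 0.3 and 0.7 give the same result. The detectable difference is SE × (1.960 + 0.842) for 80% power at two-sided 0.05.

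| π | N | SE (SD units) | Detectable difference (SD units) |
|---|---|---|---|
| 0.5 | 165 (one arm) | 0.156 | 0.44 |
| 0.5 | 495 (pooled) | 0.090 | 0.25 |
| 0.3 or 0.7 | 165 (one arm) | 0.170 | 0.48 |
| 0.3 or 0.7 | 495 (pooled) | 0.098 | 0.28 |

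With 150 evaluable patients per arm, the detectable differences are 0.46 to 0.50 SD per arm and 0.26 to 0.29 SD pooled (N = 450). The ratio is unchanged.

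**Power for an illustrative difference.** If the true difference were 0.3 SD (an assumption; the documents give no expected value), power would be 42% to 49% in one arm and 86% to 92% pooled.

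**The case against.** Several objections carry weight.

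- **The per-arm analysis is not wrong.** A reader might infer that the standard errors are incorrect or that data are thrown away. Neither follows. Each per-arm standard error is right for its own estimate, there is no bias, and every patient is analysed. Combining the three estimates by inverse variance would recover almost all the precision (simulated SE 0.0895, against 0.0889 pooled). The plan, however, does not provide for that combination.
- **The sentence covers more than infiltrates.** It also governs markers against the 3-level probability of pneumonia. If that rating is the treating clinician's, it depends on the image shown, and a by-arm analysis is defensible. This stands and limits the fix.
- **The marker SAP is not available.** It may already specify pooling. But SAP section 1 assigns it only the association with adjudicated pneumonia, so this does not settle the infiltrate analysis.
- **A by-arm rule does not forbid an overall estimate.** That is true, but none is planned.
- **Readers may know whether their report will be concealed**, since Protocol section 3.3 has staff told about the blinding. In principle this could influence a reading. By-arm results kept as description, or an arm term in the model, would deal with it.

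Three stronger readings are tempting but unsupported. First, that three tests per marker give a 14% false-positive risk (1 − 0.95³ = 0.143): this holds only if there is no association in any arm. Second, that differences between arms would be read as differences between strategies: item 11 plans no such comparison. Third, that each arm would define infiltrate by its own modality: the documents do not say so. What is true is that they name no modality or reader for it.

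**Conclusion.** The point holds as a minor gain in precision at no cost. For the marker–infiltrate association, each per-arm standard error is about 1.73 times that of a pooled estimate. The detectable difference is 0.44 to 0.48 SD per arm, against 0.25 to 0.28 SD pooled.

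The ratio assumes equal arms, similar completeness of CRP and PCT across arms, and the same association in each arm, which randomisation supports. The absolute figures also assume 30% to 70% infiltrate prevalence and 165 patients per arm with complete data.

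Pooling also fits the sponsor's own approach: SAP section 8.2.3.1 evaluates the imaging specialists' readings in the whole full analysis set without regard to arm.

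The argument covers admission values only. The SAP schedule (section 3.4) also marks laboratory tests at discharge from acute care, and item 11 does not say which value is used. Values taken after allocation could reflect management and would not support the same reasoning.

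**What to change.** In the SAP that covers the marker analyses, state for the infiltrate analysis only:

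> The association of admission CRP and PCT with infiltrate will be estimated in all randomised patients pooled across arms, adjusted for centre, for each imaging modality's infiltrate reading, with one modality (for example LDCT) named as main. By-arm results will be descriptive.

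The choice of main modality is the sponsor's. LDCT would be consistent with the Protocol synopsis, which defines viral pneumonia by an infiltrate on CT. The same text should say whose reading defines an infiltrate.

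Keep the by-arm rule for markers against the 3-level probability of pneumonia where the rating is the treating clinician's, and say in that SAP whose rating is used.

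The cost is a sentence or two of text. No new data are needed, and the by-arm results remain available.
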